1. SPECIFIC AIMS

The proposed pilot study is an exploratory implementation and mixed methods evaluation of self-guided repetitive art-making to assess the impact of this artistic practice on 1) self-reported pain levels, 2) self-reported mood states including anxiety and depression, and 3) self-reported feelings of connection for patients living with chronic pain and opioid use disorder (OUD) or documented misuse of opioids. A secondary research focus will be to assess whether viewing art made by patients with chronic pain and OUD/opioid misuse diminishes stigma towards these populations for the broader population.

Aim 1 (Acceptability): Develop three (3) self-guided repetitive artmaking kits for patients with chronic pain and OUD/opioid misuse to use on their own, with instructions in English and Spanish, and train the patients on the use of these artmaking kits through three (3) in-person workshops in English and Spanish. *Hypothesis 1: Simple art kits that offer repetitive artmaking practices will be acceptable for and interesting to patients with chronic pain and OUD/opioid misuse.* Acceptability will be measured by whether patients complete the pre- and post-survey and/or whether they report to the Study Coordinator during monthly check-ins that they have engaged with the art kit(s). At least 80% of patients will report using an art kit on their own (via self-report on surveys, to be supplemented by Study Coordinator text check-ins and storytelling data for patients who participate in the final showcase event). We will ask brief questions at the workshops to assess patients' previous experience with art and openness to mindfulness activities, along with a brief demographic questionnaire, to provide a baseline.

Aim 2 (Efficacy): Evaluate whether the self-guided repetitive artmaking kits significantly impact patients' self-reported experiences of pain, mood (inclusive of depression and anxiety), and social isolation. *Hypothesis 2: Repetitive artmaking will reduce experiences of pain for patients with both chronic pain and OUD/opioid misuse.* Acceptance criteria: Significant pain reduction during artmaking practice as captured using the first three questions of the BPI Reduced Minus Peg Questions 8-item questionnaire (attached) – questions one and two will be only asked in the pre-survey as these questions ask about pain over the last week and will therefore not change before and after a solo artmaking experience. We also propose to have patients complete the 6-item Pain Catastrophizing Questionnaire (attached) during the in-person workshop to gain an understanding about patients' experiences of pain. This data will be supplemented with qualitative data from the meaning making session and storytelling content, for those who participate. *Hypothesis 3: Repetitive artmaking will reduce depression and anxiety and improve mood for patients with chronic pain and OUD/opioid misuse.* Significance improvements in mood (anxiety and depression) during artmaking practice as captured using single survey questions asking patients to rate their current experiences of anxiety and depression. This data will be supplemented with qualitative data from the meaning making session and storytelling content, for those who participate. *Hypothesis 4: Supporting patients with chronic pain and OUD/opioid misuse in making art will result in higher ratings of social connectivity.* Significant improvement in social connectivity during artmaking practice as captured using the IOS-CC (attached). *Hypothesis 5: Repetitive artmaking will reduce opioid misuse in patients.* Any reduction in non-prescribed opioid use as captured by a question asking patients if they have used non-prescribed opioids in the past 24 hours (modified from the Addiction Severity Index question about recent opioid use) as both a measure of opioid use in connection with artmaking and we will be evaluating patients' opioid use over the course of the study, and a question asking patients to share how high they are at the time of the survey (from the Modified DFAQ-CU Inventory but focusing on opioids not cannabis). This

data will be supplemented with qualitative data from the meaning making session and storytelling content, for those who participate.

Aim 3 (Community Intervention): Prepare an exhibit of art made by patients and stories of their experiences and evaluate whether this exhibit impacts stigma regarding chronic pain and opioid use in the broader population (audience). *Hypothesis 6: Laypersons viewing photographs of the art paired with patients' descriptions of their art and the artmaking process, will lessen stigma towards people with chronic pain and OUD/opioid misuse.* Laypersons who view the exhibit and who complete a retroactive pre-post survey will self-report lessened stigma towards persons with chronic pain and OUD/opioid misuse through positive appraisal of the artists.

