3. RESEARCH DESIGN AND METHODS

Overview:

The proposed pilot is an exploratory evaluation of whether repetitive artmaking in home environments is acceptable for chronic pain self-management in individuals with OUD/opioid misuse, and whether self-driven repetitive artmaking can offer respite from pain, depression, and anxiety, and improve social connectivity. The study will recruit approximately 40 individuals living with chronic pain with an OUD diagnosis or opioid misuse from a Montefiore-led methadone clinic, [name]. The Principal Investigators (PIs) will collaborate with an Art Therapist to develop three (3) simple art kits. Patients will participate in an in-person art workshop, to be held in English with the support of a Spanish translator, and complete pre- and post-surveys assessing in-the-moment pain, anxiety, depression, and social connectivity. Patients will be given all three (3) kits to take home and offered financial incentives to complete the same pre- and post-surveys and art kits at home up to four (4) times within a four-month period to assess real-world adoptability and efficacy. The art kits will not include any visible information about Montefiore or the study in the front of the packets; paper versions of the survey will be enclosed within the kits, to support confidentiality. All patients will be invited to a virtual meaning making group to capture qualitative feedback. The study staff will not share the names of patients with anyone outside the core research team – the co-PIs, Study Coordinator, Patient Advocate, Biostatistician, Art Therapist, and Photographer and Exhibit Coordinator. All patients will be invited to have their art photographed and share their experience of the artmaking process and how it relates to their chronic pain and opioid use. Photographs and stories will be shared on the Montefiore campus as an art exhibit, and the layperson audience will be surveyed to assess any resultant alteration in feelings of stigma toward the population of those living with chronic pain and OUD/opioid misuse. Patients who share their artwork will be able to decide if they want their name (or a portion of their name) or a pseudonym to be included in the exhibit alongside their artwork, or if they would like to maintain anonymity.

Implementation:

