In-Person Workshop: [name], an Art Therapist, will lead three (3) two-hour in-person workshops at [name], with all patients required to attend one (1) in-person workshop as part of this study. Spanish translation will be available at all workshops. The purpose of these workshops are twofold: they will gather patient characteristic data (demographics, Pain Catastrophizing Survey, questions on experience with art and openness to mindfulness) and orient patients to the use of the art kits available to them to take and use at home. The art therapist will develop three (3) repetitive artmaking kit options and will develop enough for patients to leave the workshop with one of each kit. Preliminary options include mandala painting and macramé, with the final kits to be developed during the planning phase in partnership with the IMPOWR-ME Community Leadership Board. As previously stated, the art kits will be compiled to minimize visual identification from others that they are part of a research study, with all survey materials asking sensitive questions buried in the middle of the packet. At the start of the in-person workshop, the PI will orient patients to the pilot goals and activities, answer all questions, collect consent forms, and provide the link to the pre-survey assessing pain and mood as well as paper versions of the survey. [name] will provide an engaging overview of the three available kits, and patients will select a kit to try for the in-person workshop. [name] and the Study Coordinator will be present to provide Spanish translation and explanation as necessary. The last 15 minutes of the workshop will be saved for patients to complete the post-survey on pain and

mood and to remind patients that they will be compensated for using the art kits at home up to four (4) times if they complete pre- and post-surveys. Finally, patients will be informed that they will be invited to bring their artistic outputs to be photographed by a professional photographer ([name]) at the end of the four-month period and to share their experiences of making the art, so that they can share what they have made with the broader community. It will be made it clear that displaying their art and sharing their experiences is not mandatory, that patients do not need to decide during the workshop if they will want to share their artwork, and that they will be able to use full, part, or none of their name in the event.

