At-Home Artmaking: Patients will be invited to take home all three (3) art kits at the end of the in-person workshop, each of which will allow them to make multiple versions of the type of art in question (aka materials for multiple mandalas). Each kit will include multiple copies of the pre- and post-survey assessing pain and mood and a reminder to complete the pre- and post-survey when doing the kits to receive an incentive of \$20 compensation for up to four (4) times within a four-month period (the end date will be included in the art kits). Communication from the Survey Coordinator will also include the links to the pre- and post-surveys. The instructions will prompt patients to complete the survey immediately before starting the art kit and immediately after concluding. Patients will further be prompted to include a photo of their art in the post-survey if they are using the online survey system, or they can text their photo to the Study Coordinator if they have phone-based photography capacity. All instructions will be in English and Spanish. This implementation process is designed to assess real-world use of the art kits.

Data Collection:

Event	Data Collection Method	Measures to be Collected
In-Person Workshop	Patients complete online pre- and post-survey via a QR code or paper form	
 • Questions 1-3 of the BPI Reduced Minus Peg Questions (pre) and question 3 of the BPI Reduced Minus Peg Questions (post) • Pain Catastrophizing Questionnaire • Single question asking about current level of depression • Single question asking about current level of anxiety • IOS-CC • Questions asking about current and recent unprescribed opioid use (pre) and level of highness in the moment (pre, post) • Single question asking about experience with art • Single question asking about openness to mindfulness activities
At-Home Artistic Practice #1	Patients complete paper pre- and post-survey	
 • Questions 1-3 of the BPI Reduced Minus Peg Questions (pre) and

At-Home Artistic Practice #2		question 3 of the BPI Reduced Minus Peg Questions (post) 
 • Single question asking about current level of depression • Single question asking about current level of anxiety • IOS-CC • Questions asking about current and recent unprescribed opioid use (pre) and level of highness in the moment (pre, post)
At-Home Artistic Practice #3		
At-Home Artistic Practice #4		

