Check-in Texts & Calls	The Study Coordinator will text all patients one (1) month after the in-person workshop and every one (1) month thereafter for a total of four (4) connection points to assess any barriers to at-home engagement; for those patients who do not respond to texts, the Study Coordinator will complete phone calls and document in Redcap	
 • Question asking whether patients used the art kits in the past month • Documentation of any barriers • Brief qualitative data
Meaning Making Session	All patients will be invited to join a two-hour virtual meaning making session	
 • Rich qualitative data of their experience of the art kits and solo repetitive artmaking
Exhibit	Exhibit viewers (laypersons) will complete an online post-survey via QR code that captures reactions before/after viewing the exhibit	
 • Short set of stigma questions to be developed

Most data will be collected online, via an online survey that automatically populates into a password protected spreadsheet. The Patient Advocate or Study Coordinator will collect all paper surveys during routine treatment at [name] and provide them to the Study Coordinator, who will clean and manually input the data.

Data Analysis:

Analysis will be conducted through a mixed-methods approach. Quantitative analysis to test hypotheses 2-5 will be led by [name], Biostatistician, who will report changes from pre- and post-surveys on all the measures provided to patients and exhibit viewers. For bivariate analyses, he will use paired t-tests. For multivariate analyses, he will employ control variables from baseline, such as demographic variables, and conduct linear regressions. Qualitative analysis to test hypotheses 1-5 will be led by the co-PI, who will code all qualitative data collected from patients (open-ended questions in all surveys, transcript from the meaning making session) to

surface themes that can provide phenomenological or experiential data. Drs. [name] and the co-PIs will collaborate to develop a final report that includes both quantitative and qualitative data.

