6. INFORMED CONSENT

Informed consent will be conducted by the Study Coordinator as follows: all potential patients will complete a brief oral consent and then complete the eligibility screener. This process can take place in-person in a private room at [name] or over the phone in the case of patients who wish to be screened at a time of their choosing as opposed to when they encounter the study team. If eligible, the Study Coordinator will explain the study and any risks and benefits, and obtain written informed consent.

Remuneration:

Patients will receive \$50 for participating in the in-person workshop and will be incentivized to use the art kits at home and complete pre- and post-testing for up to four times with \$20 each time. Further, all patients will be invited to participate in a meaning making session to capture qualitative feedback on the feasibility of the project; if they attend, they will be compensated \$50 for their participation. Patients will be compensated through a Clincard in their name. These cards include no information that link them to the study or indicate that this compensation is related to a study.

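### Aim 1's 80% acceptability target pools paid home sessions with check-in reports, so it shows uptake while payment was offered; use beyond the paid sessions should be reported beside it

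*Combined protocol and SAP*

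**What the plan says.** Aim 1 (section 1) lets either of two sources establish acceptability: "Acceptability will be measured by whether patients complete the pre- and post-survey and/or whether they report to the Study Coordinator" at the monthly check-ins that they engaged with a kit. The numerical target is "At least 80% of patients will report using an art kit on their own". Its source is given as "via self-report on surveys, to be supplemented by Study Coordinator text check-ins", plus storytelling from those who join the final showcase. No minimum number of sessions is set. The definition does not say whether the survey pair completed at the workshop counts.

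Home survey pairs are paid. Under In-Person Workshop in section 3, patients are reminded that "they will be compensated for using the art kits at home up to four (4) times if they complete pre- and post-surveys". Under Remuneration in section 6, they "will be incentivized to use the art kits at home and complete pre- and post-testing for up to four times with" $20 each time. The Overview in section 3 links these incentivised sessions to a purpose: they are offered "within a four-month period to assess real-world adoptability and efficacy". The At-Home Artmaking text ends: "This implementation process is designed to assess real-world use of the art kits".

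The only other listed quantitative measure of use is in the check-in row of the Data Collection table, asked at four monthly contacts: "Question asking whether patients used the art kits in the past month". No payment is listed for answering it.

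The Data Analysis text assigns quantitative analysis to hypotheses 2 to 5 and qualitative analysis to hypotheses 1 to 5.

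**The concern.** The kits are meant for self-management at home, outside clinical care. The main source for the 80% is a set of surveys that patients are paid to complete around a kit session, and by the plan's own wording the payment covers using the kit as well as the paperwork. A patient who used a kit once for $20 and a patient who used kits throughout the four months count the same.

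The 80% is Aim 1's only numerical target. If it is reached, the wording in section 3 invites readers to take it as real-world adoption. A follow-on programme that does not pay for sessions needs to know how much use went beyond the paid sessions, and the planned figure does not say.

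**Working it through.** **Inputs.** Target 80% (section 1, Aim 1). About 40 workshop completers, possibly more (section 4). $20 per home survey pair, at most four pairs (sections 3 and 6). Four monthly check-ins with one question on use in the past month (section 3). The plan gives no null rate, alpha or power for the 80%, so it is a benchmark with no derivation to reproduce.

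**Step 1: what meets the target.** 0.80 × 40 = 32 patients; 31/40 = 77.5% falls short. The exact (Clopper-Pearson) 95% interval for 32/40 is 64.4% to 90.9%.

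**Step 2: the least paid activity that is enough when no one uses a kit outside a paid session.** Payable sessions: 40 × 4 = 160. One from each of 32 patients: 32/160 = 20%. Payments: 32 × $20 = $640 out of 160 × $20 = $3,200. The share stays at 20% with more patients: 36/180 for 45 patients and 40/200 for 50.

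**Step 3: the opposite extreme.** Because of the and/or rule, 32 patients who report use at check-ins and file no survey pair also meet the target, with no paid sessions. The pooled figure is therefore compatible with anything from no use beyond paid sessions to unpaid use only.

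**Step 4: what one pooled result can hide.** The documents give no figure for use beyond paid sessions, so the rows below are assumptions. All of them go with a pooled 32/40 = 80%.

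| Patients with any use beyond paid sessions (assumed) | Share of 40 | Exact 95% CI |
|---|---|---|
| 0 | 0% | 0% to 8.8% |
| 8 | 20% | 9.1% to 35.6% |
| 16 | 40% | 24.9% to 56.7% |
| 32 | 80% | 64.4% to 90.9% |

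**Step 5: what linkage would recover.** Let Y be the number of check-ins at which a patient says yes (0 to 4) and P the number of paid home pairs (0 to 4). A paid pair can account for at most one month, so the number of months with unpaid use is at least max(0, Y − P).

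- Y = 1, P = 0: at least 1 month.
- Y = 4, P = 1: at least 3 months.
- Y = 1, P = 1: bound 0.
- Y = 4, P = 4: bound 0.

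This assumes that answers are accurate and that the first check-in answer does not refer to the workshop session. Dated pairs would allow month-by-month matching, but the documents do not say that paper surveys are dated. Even with dates, unpaid use in a month that also has a paid session stays hidden.

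**Step 6: a separate quantity.** How many patients would have used a kit had no payment been offered is a different question. If 0, 3, 8 or 16 of the 32 were payment-only users (assumed), uptake without any offer would be 32/40 = 80%, 29/40 = 72.5%, 24/40 = 60% or 16/40 = 40%. A study in which everyone is offered payment cannot estimate this number.

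**The case against.** The strongest reply is that the data to inform the point are largely there. All patients are checked on four times, non-responders to texts are phoned, and patients have IDs (section 8). A yes from someone with no paid pair indicates unpaid use, and two or more sessions can already be counted from the home surveys. This stands. A reader might infer that the study cannot separate paid from unpaid use at all; the documents do not support that. What remains is a linkage the plan does not describe, which yields only the lower bound in Step 5.

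A reader might also infer that the 80% consists only of paid use. The and/or rule shows otherwise, which is why a label such as uptake with payment would be wrong for patients who qualify only through a check-in.

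It is also fair to say that Aim 1 does not itself attach real-world to the 80%; the phrase describes the home phase, in contrast to art therapy in formal settings. But the Overview joins it to the incentivised sessions, and the 80% is the only target set for their use.

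Two further inferences fail. One is that attending the workshop satisfies the target through the workshop survey pair; the target sentence requires use on their own, so at most the definition needs tidying. The other is that interest in the kits goes unexamined. The co-PI's qualitative analysis covers hypothesis 1, drawing on open-ended survey questions and the meaning making session, so adding numerical ratings would be a preference.

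Finally, this is an exploratory pilot and paying participants is ordinary. Both are true, and neither the payments nor the sample size needs to change.

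**Conclusion.** The point holds as a limit on interpretation; it is not an error of calculation. As defined, the 80% measures uptake while payment was offered. For 40 patients it can be reached with 32 of 160 payable sessions and no use beyond them, and the same result is compatible with use beyond paid sessions anywhere from 0% to 80% of patients. Existing data, if linked, would narrow that range from below only.

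The documents do not show that payment inflates the figure, or by how much. Upward bias relative to unpaid use is plausible, but the figures in Steps 4 and 6 are assumptions and include no effect. The arithmetic rests on 40 workshop completers and on one home session being enough to count, since no minimum is set.

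**What to change.** 1. In Aim 1 and the section 3 Overview and At-Home Artmaking text, describe the 80% as uptake while payment was offered, and do not present it by itself as real-world use.
2. Add to the existing monthly check-in item whether, in that month, the patient used a kit at home on any occasion without completing a paid survey.
3. State that the workshop survey pair does not count as use on their own.
4. In Data Analysis, report descriptively with exact 95% confidence intervals, over all workshop completers given kits: (a) at least one paid home pair; (b) use reported at a check-in with no paid pair; (c) any use beyond paid sessions; (d) use on two or more occasions. Patients with no report stay in the denominator. Groups (a) and (b) do not overlap and together make up the pooled figure, apart from anyone identified only through storytelling, who should be shown separately.
5. State the limits of (c): a willing patient may file a paid survey for each session and so report no unpaid use, so (c) may understate willingness to use a kit without payment. It also rests on one-month recall.

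The cost is a few words in one check-in item and short edits to three parts of the protocol. Payments, visits and sample size stay as they are. The downside is slightly longer check-ins and a less favourable figure beside the 80%. The item has to be in place before the first check-ins, because use that is not asked about at the time is hard to recover later.

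### The Aim 1 acceptability measure does not exclude the workshop, so it does not match the 80% target, which is limited to use on the patient's own

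*Combined protocol and SAP*

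**What the plan says.** Two consecutive sentences in Section 1, Aim 1 govern acceptability.

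- **The measure:** "Acceptability will be measured by whether patients complete the pre- and post-survey and/or whether they report to the Study Coordinator during monthly check-ins" (the report being one of kit use). Either route is enough, and neither is tied to a place.
- **The target:** "At least 80% of patients will report using an art kit on their own", taken from self-report on the surveys and supplemented by check-ins and storytelling data.

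Section 3 describes how the surveys and check-ins arise.

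- **Workshop:** the In-Person Workshop text has it "with all patients required to attend one (1) in-person workshop as part of this study". There, "patients will select a kit to try for the in-person workshop". The pre-survey is provided at the start, and "The last 15 minutes of the workshop will be saved for patients to complete the post-survey".
- **Home:** the Overview says that patients are paid to "complete the same pre- and post-surveys and art kits at home" up to four times in four months. The kit instructions ask them to "complete the survey immediately before starting the art kit and immediately after concluding".
- **Check-ins:** "The Study Coordinator will text all patients one (1) month after the in-person workshop" and monthly after that, four contacts in all. The Data Collection table describes the item as kit use over the preceding month. It gives the purpose of the contact as finding barriers to engagement at home.

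**The concern.** Aim 1 asks whether patients will take up the kits unsupervised. The measure sentence can be satisfied by something else, namely a survey pair completed in a facilitated session that is required for participation and paid at $50 (Section 6, Remuneration). An analyst who follows that sentence and an analyst who follows the target sentence would report different proportions from the same data, and the protocol supports both.

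The target sentence does not settle the matter in practice. It is to be scored mainly from the surveys, yet the survey measures in the Section 3 Data Collection table include no question on using a kit on one's own. Own use has to be inferred from a completed survey pair, and nothing says that workshop pairs are left out of that inference. The Data Analysis text assigns Hypothesis 1 to the qualitative work and gives no scoring rule.

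Counting workshop pairs adds a way to qualify and removes none, so the discrepancy can only make the result look better.

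**Working it through.** The 80% is a chosen target. The plan gives no calculation behind it, so there is no figure to reproduce. The check is whether the measure and the target count the same patients.

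**Inputs from the documents**
- About 40 workshop completers, possibly more (Section 4).
- Target 80% (Section 1, Aim 1), which for 40 patients is 0.80 × 40 = 32.
- Workshop attendance required, with a kit tried and a survey pair requested (Section 3, In-Person Workshop and Data Collection table).
- Four check-ins, the first one month after the workshop (Section 3, Data Collection table).

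**Step 1: who qualifies under each sentence**

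| Patient | Measure, read literally | Target, as worded |
|---|---|---|
| Workshop survey pair, no later use | counted | not counted |
| Workshop survey pair, later own use reported | counted | counted |
| No workshop pair, own use reported by home survey or check-in | counted | counted |
| No workshop pair, no later use | not counted | not counted |

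The two differ only in the first row, and always in the same direction.

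**Step 2: how the literal measure behaves**

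Let w be the share of completers with a workshop survey pair and h the share with own use reported. The literal proportion is at least w, whatever h is. If the two are independent, it is 1 − (1 − w)(1 − h). The documents give neither w nor h, so the values below are assumptions.

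| Assumed w | h = 0% | h = 25% | h = 50% | h = 70% |
|---|---|---|---|---|
| 80% | 80% | 85% | 90% | 94% |
| 90% | 90% | 92.5% | 95% | 97% |
| 100% | 100% | 100% | 100% | 100% |

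Example: w = 90%, h = 50% gives 1 − 0.10 × 0.50 = 95%. At w = 90%, raising own use from 0% to 70% moves the literal measure only from 90% to 97%. The target, as worded, would move from 0% to 70%. The literal measure therefore says little about own use.

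**Step 3: the check-in item**

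A look-back of one month from a contact made one month after the workshop ends at about the workshop day. Whether the workshop falls inside it depends on the exact contact date. The second, third and fourth check-ins cannot reach it. One of four contacts is exposed, and only at the edge of its window.

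**The case against.** The strongest reply is that the intent is not in doubt. The only numerical criterion is limited to use on the patient's own, and a facilitated session is not that. The Section 3 Overview frames the question as acceptability in home environments, and the At-Home Artmaking text says that the home phase is there to assess real-world use. Workshop and home surveys are listed as separate events, the workshop form carries extra items, and Section 8 names the two sources separately, so the data can be told apart.

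All of this stands, and it rules out a stronger reading that a reader might infer: that the 80% target could be declared met with no home use. To get there one must take the numerator from the measure sentence and the threshold from the target sentence. The documents do not instruct that.

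A reader might also infer that the check-in item could seriously inflate the result. The documents do not support this either. The table gives a description and not the script, the stated purpose of the contact is engagement at home, and for the target the check-ins only supplement the surveys. No rate of mistaken affirmative answers can be taken from the documents.

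What the reply leaves untouched is that the sentence defining the measure has no such limit, and that no listed survey item supplies it. That the data are separable makes the correction easy, but does not say which pairs count.

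**Conclusion.** The point holds as a mismatch between an open measure and an own-use target. Read literally, the measure would be met by nearly every workshop completer whatever their later use, provided that most complete both workshop surveys. That proviso is an assumption, though a reasonable one given required attendance and reserved time. The difference from the own-use proportion can only be upward. Its size cannot be derived from the documents, and the table of assumed rates shows direction and insensitivity, not a forecast. The check-in overlap is minor. No design figure changes. For an exploratory pilot this is a clarification that should be made before acceptability is scored, because it decides what the main Aim 1 result means.

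**What to change.** - **Measure (Section 1, Aim 1):** state that acceptability means at least one kit use on the patient's own after the workshop, shown by an at-home pre/post survey pair, a check-in report or storytelling data, and that workshop surveys do not count. Keeping own use as the criterion, and not use at home, preserves the scope of the existing target.
- **Check-in item (Section 3, Data Collection table):** ask about use on the patient's own since the workshop at the first contact, and since the last check-in at later ones.
- **Reporting (Section 3, Data Analysis):** give the proportion among workshop completers and set it against 80%.

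The cost is a few wording changes, with no new data collection and no change to sample size. The downside is that the reported figure may be less favourable than under the literal measure.
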